5.4 SCREEN FAILURES

Screen failures are defined as participants who consent to participate in this study but are subsequently not assigned to the intervention or included in the study.

Participants who do not meet the eligibility criteria will continue to receive standard healthcare from their primary care team. Failure to participate in this study will not affect the patient’s usual treatment or follow-up in any way.

This protocol does not include provisions for re-screening participants if their circumstances change and they subsequently meet the eligibility criteria.

5.5 STRATEGIES FOR RECRUITMENT AND RETENTION

The recruitment strategy includes:

1. Initial identification from patients’ medical records to search for potential participants who meet the inclusion criteria.
2. Manual clinical confirmation by a physician external to the project, using the Shared Clinical History, to verify that selected candidates do not meet any exclusion criteria.

3. Contact with potential participants via telephone call, followed by an in-person visit to obtain signed informed consent.

Participation in the intervention is voluntary, and no material or financial incentives are provided.

No specific patient retention plan is included. Follow-up visits will be conducted as scheduled in the protocol. Appointment reminders will be provided, and during the visits, participants will receive positive reinforcement regarding the benefits of the intervention and their participation.

This protocol does not specifically include vulnerable populations. However, if during the course of the study a participant becomes part of a vulnerable group, their continued participation will be evaluated, prioritizing the participant's health and safety.

6 STUDY INTERVENTION(S) OR EXPERIMENTAL MANIPULATION(S)

6.1 STUDY INTERVENTION(S) OR EXPERIMENTAL MANIPULATION(S) ADMINISTRATION

6.1.1 STUDY INTERVENTION OR EXPERIMENTAL MANIPULATION DESCRIPTION

This protocol describes an intervention focused on lifestyle changes, with the primary objective of achieving remission of T2DM. This goal is intended to be accomplished through modifications in patients' lifestyle factors, such as dietary patterns and regular physical activity.

Remission is considered achieved when HbA1c is < 6.5% for at least 6 months, including a minimum of 3 months without antidiabetic pharmacological treatment.

The control group will receive standard care for T2DM in the primary care setting.

6.1.2 ADMINISTRATION AND/OR DOSING

The intervention program will be conducted over a period of 6 months, with a final follow-up 12 months after the end of the intervention. Participants assigned to the intervention group will receive:

- Low-carbohydrate dietary plan, adapted to the Mediterranean diet.
- Promotion of physical activity, including light and progressive strength exercise plans.
- Dietary monitoring and logging.
- Follow-up of progress and relevant parameters measured during the intervention.

The intervention will be delivered by a family physician and the evaluations of the adherence to the program will be monitored by the intervention team, consisting of a family physician, nurse and nutritionist. Sessions will take place at the primary care centers (CAP Barceloneta and CAP Larrard).

6.2 FIDELITY

6.2.1 INTERVENTIONIST TRAINING AND TRACKING

This protocol includes internal training for the intervention staff to ensure proper implementation of the program and fidelity to the outlined activities. Training will be provided prior to the start of the intervention and will include:

- Education on low-carbohydrate diets and their clinical application.
- Protocols and guidelines for conducting the intervention sessions.
- Procedures for maintaining intervention records.
- Training on the procedures for aortic imaging tests.

Any changes to the procedures described above will be officially documented and agreed upon with the intervention team.

6.3 MEASURES TO MINIMIZE BIAS: RANDOMIZATION AND BLINDING

The process of randomization and group assignment will be carried out through a randomization system with a 1:1 allocation ratio. However, due to the nature of the present study, no blinding of participants or professionals is planned, as this is a behavioral intervention and blinding would be counterproductive to the development of the research.

On the other hand, in order to minimize potential biases:

- An external analysis will be conducted by professionals who are not involved in the screening or in the implementation of the intervention activities.
- Patient screening and randomization will be performed by a team of professionals independent from the intervention group.

6.4 STUDY INTERVENTION/EXPERIMENTAL MANIPULATION ADHERENCE

To monitor and promote participant adherence to the intervention activities, biweekly telephone contacts will be conducted. During these contacts, the following will be performed:

- 24-hour dietary recall survey: using photographs of the participant's food intake over one day, their diet will be recorded.
- Overall health check of the participant.
- Review and adjustment of daily exercise plan.

A participant will be considered adherent to the intervention if they complete the initial session and at least 70% of the follow-up sessions. All adherence information will be recorded in the official intervention log.

6.5 CONCOMITANT THERAPY

During the study, participants will be allowed to continue their usual treatment for concomitant conditions. However, the use or initiation of weight-loss medications (such as GLP-1 receptor agonists) or diets other than those specified in this protocol will be prohibited, as this constitutes an exclusion criterion for the intervention. Use of concomitant medications will be recorded at each study visit.

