4 STUDY DESIGN

4.1 OVERALL DESIGN

The study is designed as an open-label, randomized clinical trial. The strategy includes Group A – Intervention, which will undergo the CREDOenAP program, and a parallel control group, Group B – Control, which will receive standard T2DM care from a primary care team (family physicians

and nurses) without any intervention from the research team, except for data collection at baseline and at the end of each study phase.

The study has been designed to evaluate the effectiveness of a lifestyle-focused intervention (CREDOenAP) on T2DM reversal in primary care patients. It is a multicenter study involving two primary care centers in Barcelona (CAP Larrad and CAP Barceloneta).

The main hypothesis is that the proposed intervention, based on a structured and culturally adapted program, is effective in achieving biochemical and functional remission of T2DM. The study design corresponds to a randomized clinical trial aimed at establishing the initial efficacy of the intervention under real-world clinical practice conditions.

Each center will recruit participants who will be randomly assigned in a 1:1 ratio to each study arm. Recruitment is planned as follows:

- Center 1 (CAP Barceloneta): Group A – Intervention (20 participants) and Group B – Control (20 participants).
- Center 2 (CAP Larrad): Group A – Intervention (40 participants) and Group B – Control (40 participants).

Group A – Intervention, comprising a total of 60 participants (20 from Center 1 and 40 from Center 2), will receive standard care plus the CREDOenAP intervention.

Group B – Control, comprising a total of 60 participants (20 from Center 1 and 40 from Center 2), will receive standard care alone.

Both Group A – Intervention and Group B – Control will include patients meeting the inclusion and exclusion criteria, with assignment conducted via stratified randomization. Potential participants will be validated by a healthcare professional not involved in the intervention to exclude false positives due to registration errors.

For stratification, performed through statistical programming, relevant characteristics that may act as potential confounding variables will be considered. In this study, stratification will be based on:

- Healthcare center (Center 1: CAP Barceloneta / Center 2: CAP Larrad)
- Sex (Male / Female)
- Age (18–50 years / \geq 50 years)
- Years since T2DM diagnosis (<5 years / \geq 5 years)

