5.2 EXCLUSION CRITERIA

The exclusion criteria for this study are as follows (meeting any of these criteria precludes participation):

1. Failure to meet the diagnostic criteria for T2DM in the screening laboratory tests.
2. Being dependent for basic activities of daily living (Barthel score ≤ 90 points).
3. Lack of willingness to cooperate with the follow-up of the lifestyle intervention plan.
4. Presence of serious or terminal comorbidities significantly worsening short- to medium-term prognosis (active cancer, terminal chronic diseases, myocardial infarction within the last 6 months, acute heart failure or NYHA stage ≥ III, etc.).
5. History of ketoacidosis.
6. Presence of criteria or potential autoimmune insulinopenia (abnormal C-peptide, anti-GAD+ antibodies, pattern of basal and/or glucose-stimulated hypoinsulinemia).
7. Cognitive impairment.
8. Weight loss exceeding 5 kg in the past 6 months.
9. Significant changes in physical activity and/or dietary patterns in the past 6 months.
10. History of eating disorders.
11. History of substance abuse.
12. History of severe psychiatric disorders.
13. Pregnancy or intention to become pregnant within the study period.

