5.3 LIFESTYLE CONSIDERATIONS

Since this study involves a behavioral intervention aimed at changing patients' lifestyle, participants must commit to following the recommendations upon which the intervention protocol is based. The restrictions and recommendations (detailed in Appendix 1) are as follows:

- Adherence to a low-carbohydrate Mediterranean diet. Participants should reduce or avoid the following:

- Processed and ultra-processed foods
- Added sugars and sweeteners (e.g., sugar, honey, syrups)
- Starchy foods (e.g., bread, pasta, rice, potatoes, legumes, cereals)
- High-fructose fruits (e.g., bananas, grapes, dates, tropical fruits)
- Fruit juices and sugar-sweetened beverages (including “zero-calorie” drinks)
- Fried foods (frying is discouraged; the only recommended oil is extra virgin olive oil, consumed raw)
- Avoid alcohol consumption
- Avoid tobacco use
- Daily physical activity:
 - Recommended 10,000 steps per day
 - Strength training (progressive and individualized): During the first two weeks, at least one hour of walking per day is recommended. Strength exercises will then be gradually introduced (e.g., two sets of 5–10 squats). Weightlifting routines may be added according to individual tolerance.
- Healthy circadian habits:
 - Maintain regular sleep schedules
 - Wake up between 6:00 and 8:00 a.m.
 - Sun exposure for 15 minutes (preferably between 7:00 and 9:00 a.m.)
 - Go to bed before 11:00 p.m.
 - Sleep approximately 8–9 hours per night
- No use of pharmacological treatments or supplements for weight or appetite control is allowed during the study.

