7.2 PARTICIPANT DISCONTINUATION/WITHDRAWAL FROM THE STUDY

Any participant may permanently withdraw from the intervention at any time without providing justification and without affecting their routine medical care. Additionally, the study team may permanently discontinue a participant's involvement in the intervention if any of the following occur:

- Loss of any contact with the participant (see Section 7.3).
- Occurrence of significant medical changes (e.g., hospitalization, new pathologies incompatible with the intervention).
- Identification of exclusion criteria that were not previously detected.
- Pregnancy or explicit intention to become pregnant.
- Initiation of therapies incompatible with the intervention.
- Evidence that the participant no longer wishes to continue the intervention activities.

Replacement of participants may be considered only if the individual was assigned to the intervention group but did not start the activities. Participants who begin the intervention and subsequently cannot continue will not be replaced.

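### Section 6.5 treats weight-loss drugs and other diets as an exclusion criterion that 5.1 and 5.2 do not list, and does not say to which arm the ban applies

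*Protocol*

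**What the plan says.** Protocol 6.5 (Concomitant Therapy) addresses participants in general. It says that "the use or initiation of weight-loss medications (such as GLP-1 receptor agonists) or diets other than those specified in this protocol will be prohibited", and gives the reason: "as this constitutes an exclusion criterion for the intervention".

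The eligibility sections do not carry this through. Section 5.1 has five inclusion criteria and section 5.2 has 13 exclusion criteria, introduced with the words "meeting any of these criteria precludes participation". None names weight-loss drugs, GLP-1 receptor agonists or a competing diet. The nearest items in 5.2 are number 8 (recent loss of more than 5 kg) and number 9 (recent marked change in activity or diet).

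Section 5.3 (Lifestyle Considerations) repeats the drug ban as an on-study restriction: "No use of pharmacological treatments or supplements for weight or appetite control is allowed during the study". It names no arm in that line.

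For the comparator, 4.1 describes a control group "which will receive standard T2DM care from a primary care team", and adds "without any intervention from the research team, except for data collection at baseline and at the end of each study phase".

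Section 7.2 lets the study team permanently end a participant's involvement when an exclusion criterion is found late, or on "Initiation of therapies incompatible with the intervention". Section 6.5.1 lets the team start drug treatment in any participant who decompensates. It sets no limit on the class and does not refer back to 6.5.

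**The concern.** An exclusion criterion that appears only in the concomitant-therapy section is not part of the list used for screening. Under 5.5, a physician outside the project checks records against the exclusion criteria. A physician who works from 5.2 will accept a current user, and the conflict with 6.5 then surfaces only after randomisation. A question that should be settled before allocation becomes one about discontinuation after it.

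The unstated arm adds a second problem. If the ban covers everyone, it limits what the control arm may receive, although 4.1 keeps the research team out of control care. If it covers Group A only, permitted background therapy differs between the arms, and a reader of the results would need to know that. The protocol commits to neither.

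At stake are the definition of the enrolled population, the definition of the comparator, and whether participants can leave the analysis because of a treatment they received after randomisation.

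**Working it through.** The point rests on text, not on a calculation, so the check is to follow typical participants through the sections.

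1. **A stable user of a GLP-1 receptor agonist at screening**, with no recent weight loss above 5 kg and no recent change of diet or activity.
   - 5.1: nothing bars this person.
   - 5.2: items 8 and 9 do not apply, and no other item mentions the drug. The person is eligible.
   - 6.5: use, not only initiation, is prohibited and is called an exclusion criterion. The person is not eligible.
   - 5.3: continued use during the study for weight or appetite control is not allowed.
   - 7.2: the team may act on an exclusion criterion that was missed earlier.
   - Result: eligible under one section and barred under another, with removal possible after randomisation. This is a direct contradiction.

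2. **A Group A participant who starts such a drug.**
   - 5.3, 6.5 and 7.2 agree that this is not allowed and may lead to discontinuation.
   - 7.1 plans continued follow-up visits, with consent, after the intervention is discontinued. 7.2 has no matching provision.
   - Result: no contradiction about the ban, but follow-up after removal is not settled.

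3. **A control participant who starts such a drug under usual care.**
   - 4.1: care is standard and the research team only collects data.
   - 5.3 and 6.5: prohibited on their face, since no arm is named.
   - 2.2 (Background) lists incretin receptor agonists among antidiabetic medications, so the named class is one that the protocol itself treats as diabetes therapy.
   - 7.2: discontinuation is possible, but the text speaks of involvement in the intervention, which a control does not receive, while the section heading speaks of the study.
   - Result: undetermined. The sections do not say whether the rule reaches this person.

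4. **A participant of either arm given rescue treatment.**
   - 6.5.1 sets no class limit and does not say how it stands to 6.5 or to the 7.2 trigger.
   - Result: undetermined.

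5. **Path to the analysis.** Section 9.3 defines the ITT set as randomised participants with completed minimum follow-up and with data at baseline, 6 months and 18 months. Section 9.4.2 defines it as everyone randomised, by allocated group. A participant removed in cases 1 to 4 whose follow-up stops falls out of the first set and stays in the second. The unclear rule on therapy can therefore reach the primary comparison through 9.3.

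**The case against.** The strongest reply is that the ban was meant for Group A. Section 6.5 says the criterion is one for the intervention, and the only diet the protocol specifies is Group A's. Section 5.3 presents its restrictions as commitments that go with a behavioural intervention. On that reading the ban does not touch standard care. The reading is reasonable, but it is nowhere stated. It also does not cure the eligibility conflict: screening comes before allocation, so a criterion for Group A still has to be applied to everyone.

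One could also say that 5.1 closes by requiring that candidates can comply with the intervention activities, and that 5.2 item 3 excludes the unwilling. Neither names these drugs, and a check of records against 5.2 would not pick up a current user.

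The discontinuation rule in 7.2 is discretionary, 7.1 foresees continued follow-up, and 9.4.2 analyses everyone randomised. All of that stands. It makes the withdrawal question an unresolved rule rather than a flat contradiction.

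Three stronger readings are tempting but not supported:

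- **That removing controls who start such a drug raises the control remission rate by a calculable amount.** The protocol gives no rate of initiation, and 7.2 does not require removal. Not every banned product is shown to be antidiabetic: 5.3 covers supplements and anything for appetite. The argument also applies only to remission, while 9.4.2 names change in HbA1c as primary.
- **That the two centres would enrol different populations.** There is one list in 5.2 and one screening procedure for both.
- **That the ban plainly contradicts standard care.** The Group A reading is open, and the protocol does not say whether standard care includes these drugs.

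**Conclusion.** The point holds for eligibility without qualification: 6.5 asserts an exclusion criterion that 5.1 and 5.2 do not contain, and a current user can be randomised under one section and barred under another. It holds for the comparator as an ambiguity: the arm is not stated, and either reading has a consequence that the protocol leaves unsaid. It holds for withdrawals as an unresolved rule, which matters because the two ITT definitions treat a removed participant differently.

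No numerical size is attached. The documents give neither the share of eligible patients already on these therapies nor the share expected to start one, and any figure would be invented. The conclusion assumes only that at least some eligible patients use or start such a therapy, as the protocol itself foresees by banning it. The correction should be made, ideally before enrolment, because eligibility cannot be repaired after randomisation.

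**What to change.** Reconcile 4.1, 5.2, 5.3, 6.5, 6.5.1 and 7.2 so that a single statement, repeated consistently, says:

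- whether current use of weight-loss medication or of another diet affects eligibility, with the entry in 5.2 made to agree with 6.5;
- in which arm or arms the on-study restriction applies, and how that fits standard care in 4.1;
- how rescue treatment under 6.5.1 stands to the restriction and to the trigger in 7.2.

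Which clinical rule is adopted is for the investigators. This review takes no position on it.

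Separately, state that whatever is decided about the intervention, a randomised participant who starts such a therapy stays in data collection, with consent as in 7.1, and in the ITT analysis of everyone randomised as in 9.4.2. The completer wording in 9.3 should be brought into line. Remission for such a participant should follow the existing endpoint definition where the drug is an antidiabetic medication.

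The cost is a protocol wording amendment and a matching line on the screening checklist. No new data, visits or sample are needed.

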6.5.1 RESCUE THERAPY

In the event of a significant glycemic decompensation in any participant (HbA1c > 9% or presence of symptoms), the study team may initiate pharmacological treatment based on clinical judgment or refer the participant to their usual physician for further evaluation. The date, type, and dose of any medication initiated will be recorded.

7 STUDY INTERVENTION/EXPERIMENTAL MANIPULATION DISCONTINUATION AND PARTICIPANT DISCONTINUATION/WITHDRAWAL

7.1 DISCONTINUATION OF STUDY INTERVENTION/EXPERIMENTAL MANIPULATION

Participation in the study is voluntary, and participants may withdraw from the intervention at any time. Additionally, the study team may decide to discontinue a participant's involvement if any of the following conditions occur:

- Non-compliance with the intervention activities.
- Emergence of new comorbidities incompatible with the intervention.
- Deterioration of health status since the start of the intervention (e.g., significant involuntary weight loss).
- Experiencing discomfort related to the intervention, whether physical or psychological.

In the event of intervention discontinuation, the following information will be recorded:

- Date of discontinuation.
- Reason for discontinuation.
- Health status at the time of discontinuation.
- Plan to continue with the scheduled follow-up visits, provided the participant consents.

7.2 PARTICIPANT DISCONTINUATION/WITHDRAWAL FROM THE STUDY

Any participant may permanently withdraw from the intervention at any time without providing justification and without affecting their routine medical care. Additionally, the study team may permanently discontinue a participant's involvement in the intervention if any of the following occur:

- Loss of any contact with the participant (see Section 7.3).
- Occurrence of significant medical changes (e.g., hospitalization, new pathologies incompatible with the intervention).
- Identification of exclusion criteria that were not previously detected.
- Pregnancy or explicit intention to become pregnant.
- Initiation of therapies incompatible with the intervention.
- Evidence that the participant no longer wishes to continue the intervention activities.

Replacement of participants may be considered only if the individual was assigned to the intervention group but did not start the activities. Participants who begin the intervention and subsequently cannot continue will not be replaced.

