The randomization sequence will be generated by an independent statistician.

The intervention has been designed to last 6 months. During this period, participants in the intervention group will receive individualized follow-up, both in-person and via telephone, aimed at achieving lifestyle changes (dietary modifications, increased physical activity, improved emotional management, etc.).

The control group will receive standard care for T2DM, with follow-up according to routine primary care practices. They will participate in periodic assessments but will not receive any components of the intervention program.

The study design includes a follow-up assessment 12 months after the end of the intervention (18 months from the start of the intervention) to evaluate the sustainability and long-term effects of the intervention.

Finally, no interim analyses or additional sub-studies are planned within this protocol.

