4.2 SCIENTIFIC RATIONALE FOR STUDY DESIGN

Evidence regarding the possibility of T2DM remission through patient-centered lifestyle interventions has generated increasing interest in replicating these results outside highly controlled settings. However, most available studies have been conducted in hospital or experimental environments, with resources that are difficult to implement or scale in primary care and at a large scale.

This protocol addresses this gap by focusing on the creation of an intervention adapted to primary care resources, where routine follow-up of T2DM patients is performed. This intervention will allow evaluation of both the effectiveness and feasibility of a program under real-world clinical practice conditions and which is using sustainable real food nutrition recommendations. Additionally, the use of a control group receiving standard care will facilitate comparison with currently available care, without introducing biases associated with placebo or other external factors.

The chosen intervention design—a block-randomized study stratified by key variables (center, age, sex, duration of diagnosis)—aims to ensure comparability between groups and minimize potential biases. The study is open-label, as blinding of participants and investigators is not feasible due to the behavioral nature of the intervention. (*Friedman et al., 2015*)

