9.3 POPULATIONS FOR ANALYSES

The populations identified to be included in the study are as follows:

Intention-to-Treat (ITT) Analysis: All randomized participants who have completed the minimum required follow-up and for whom clinical data and questionnaires are available at baseline (T0), 6 months post-intervention (T-6 months), and 18 months post-intervention (T-18 months).

Per-Protocol Analysis: Participants who have completed at least the main intervention session and for whom clinical data and questionnaires are available at a minimum of baseline (T0) and 6 months post-intervention (T-6 months).

Sensitivity Analysis: Sensitivity analyses will be performed in subgroups according to participant characteristics, including population with more than five years since T2DM diagnosis, sex, and age.

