9.4.2 ANALYSIS OF THE PRIMARY ENDPOINT(S)

The primary endpoint is the change in glycated hemoglobin (HbA1c, %) from baseline to 6 months. HbA1c is measured as a continuous variable on an interval scale. The endpoint will be calculated as the absolute difference between baseline HbA1c and the value obtained at 6 months.

The primary analysis will be performed using analysis of covariance (ANCOVA) with treatment group (intervention vs. control) as the fixed factor, and baseline HbA1c as a covariate to improve precision. Additional prespecified covariates will include age, sex, study site, and randomization block, based on their potential clinical relevance and to ensure adjustment for any residual imbalance despite randomization. A secondary, confirmatory analysis will be conducted using a

mixed-effects model for repeated measures (MMRM), which includes all available timepoints (baseline, 3 months, and 6 months). This model accounts for within-subject correlation by specifying an unstructured covariance matrix.

Results will be presented as adjusted mean differences between groups with 95% confidence intervals and corresponding two-sided p-values. Least-squares means (LSMEANS) will be used to report group means adjusted for covariates.

The Intention-to-Treat (ITT) population will be the primary analytic set, including all randomized participants according to their allocated group. A Per-Protocol (PP) population, defined as participants with at least 70% adherence to the intervention, will be analyzed as a sensitivity approach.

Handling of Missing Data; for ANCOVA, missing data at 6 months will be addressed using multiple imputation under the missing-at-random (MAR) assumption. In MMRM, missing data are implicitly handled under MAR. Additional sensitivity analyses will explore the robustness of results to different missing-data mechanisms.

For ANCOVA, residuals will be checked for normality and homoscedasticity. If these assumptions are substantially violated, transformations or nonparametric methods will be considered. For MMRM, model fit will be evaluated and alternative covariance structures tested.

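### The set that 9.3 calls ITT is a completer set and contradicts 9.4.2; separately, 7.2 allows intervention-arm non-starters to be replaced without saying how the replacement is allocated

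*Protocol*

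**What the plan says.** **Analysis sets.** Protocol 9.3 defines the ITT set as "All randomized participants who have completed the minimum required follow-up and for whom clinical data and questionnaires are available" at baseline, 6 months and 18 months. Section 9.4.2 describes the primary analytic set as "including all randomized participants according to their allocated group", and handles missing 6-month values by multiple imputation under missing at random (MAR). For per-protocol, 9.3 asks for "Participants who have completed at least the main intervention session" plus baseline and 6-month data, whereas 9.4.2 and 9.4.3 ask for at least 70% adherence.

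**Replacement.** Section 7.2 states: "Replacement of participants may be considered only if the individual was assigned to the intervention group but did not start the activities". People who start and later stop are not replaced.

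**Allocation.** Section 4.1 says "Each center will recruit participants who will be randomly assigned in a 1:1 ratio to each study arm", with stratification, and "The randomization sequence will be generated by an independent statistician". Section 6.3 adds "Patient screening and randomization will be performed by a team of professionals independent from the intervention group". None of these mentions replacements. Section 4.2 states "The study is open-label, as blinding of participants and investigators is not feasible", and the schedule in 1.3 places randomisation before the intervention session at Visit 2.

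**The concern.** An ITT set that requires later data is selected on what happens after randomisation. Under 9.3, an intervention-arm participant who never starts and does not return is left out of the comparison. So is anyone in either arm who has 6-month data but misses only the 18-month visit, even though the primary endpoint is at 6 months. Under 9.4.2 the same people are in. While both definitions stand in an open-label trial, the primary set could be chosen after outcomes are known.

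The replacement rule raises a related but smaller issue. It is discretionary, and it depends on behaviour seen after an open allocation. It also aims to refill a named arm, whereas the only allocation route described is a 1:1 stratified sequence. A newly randomised person may fall in the control arm, so the rule means either stepping outside the sequence or recruiting more people into both arms. Section 7.2 does not say which.

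**Working it through.** **The plan's own figure (9.2).** For 5% vs 25% remission, two-sided alpha 0.05 and 80% power, the average-proportion formula gives 2 × 0.15 × 0.85 × (1.960 + 0.842)² / 0.20² = 50.04, so 51 per arm. Power at the stated 52 is 82.5% (pooled normal formula), consistent with a beta below 0.2. Then 52 × 1.15 = 59.8, so 60. The figure reproduces and the point does not depend on it.

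**Inputs.** From 9.2: 60 per arm, control remission 5% (upper end of the stated 0 to 5%), intervention remission 25%. Assumed, because the protocol gives no value: a non-starter share f of 5, 10, 15 or 20% (k = 60f = 3, 6, 9, 12); starters remit at 25%, non-starters at 5%; control losses unrelated to outcome.

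**Formulas for the intervention-arm rate**
- All randomised, outcomes known: 0.25(1 − f) + 0.05f.
- 9.3 set, non-starters lacking data: 25%, whether 60 − k are analysed (no replacement) or 60 (with replacement).
- Replacements placed directly in the arm, all starting, everyone kept, non-starters' outcomes observed: [(60 − k)0.25 + k·0.05 + k·0.25] / (60 + k).

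| k of 60 | all randomised | 9.3 set | overstated by | direct replacement, all kept | overstated by |
|---|---|---|---|---|---|
| 3 | 24% | 25% | 1 point | 24.05% | 0.05 |
| 6 | 23% | 25% | 2 points | 23.18% | 0.18 |
| 9 | 22% | 25% | 3 points | 22.39% | 0.39 |
| 12 | 21% | 25% | 4 points | 21.67% | 0.67 |

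If new recruits are randomised 1:1 and all are analysed as allocated, the added bias is 0.

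**Direct replacement with no programme effect.** Take 5% remission overall, none in non-starters and 0.05/(1 − f) in starters. The arm's rate becomes 0.05/(1 − f²), an excess of 0.01, 0.05, 0.12 and 0.21 points. The favourable false-positive rate (pooled z, exact enumeration) moves from 2.44 to 2.46%, 1.89 to 1.94%, 2.21 to 2.38% and 1.81 to 2.05%.

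**Does adopting 9.4.2 remove the 1 to 4 points?** Not by itself. Its listed covariates are baseline HbA1c, age, sex, site and block, with no indicator of having started. If the imputation model uses only arm and those covariates, missing non-starters are imputed near the starters' 25%. In the limit the arm rate is [(60 − k)0.25 + k·0.25]/60 = 25%, the same as the 9.3 set.

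**Power (pooled normal formula, control 5%, non-starters' outcomes observed)**

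| k | no replacement, 60 vs 60 | replace and keep, 60 + k vs 60 | k extra per arm, randomised 1:1 |
|---|---|---|---|
| 0 | 87.6% | – | – |
| 3 | 84.9% | 85.8% | 86.6% |
| 6 | 81.9% | 84.0% | 85.5% |
| 9 | 78.5% | 82.1% | 84.0% |
| 12 | 74.7% | 80.1% | 82.1% |

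All figures are for remission, on which 9.2 is sized. For HbA1c change, the endpoint named in 9.4.2, the protocol gives no SD or expected difference, so no size can be stated.

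**The case against.** A reader might infer from 7.2 that the team will place replacements straight into the intervention arm and seriously bias the trial. The documents do not support that. Sections 4.1 and 6.3 describe only stratified randomisation run by an independent team, and no text permits direct placement. Section 7.2 says only that replacement may be considered. Even under the adverse reading the bias stays below 1 point. What stands is the silence on how a vacancy in one named arm would be filled.

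A reader might also object that controls have no matching rule. The trigger is not starting the programme's activities, and controls have none to start, so the asymmetry alone is not an error.

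Nor do the definitions put every replaced person out of one ITT set and into the other. Neither 9.3 nor 9.4.2 mentions replaced participants, and a non-starter who attends every assessment could meet both. Exclusion criterion 3 screens out unwillingness before entry, 7.1 plans continued visits where the participant consents, and 8.1 describes the laboratory tests as routine care. The conflict affects people without later data, and these provisions should keep their number down.

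The strongest objection is that the 1 to 4 points belong to the completer definition, not to replacement, and that copying 9.4.2 into 9.3 would leave most of them in place under MAR imputation that ignores whether a person started. That is correct, and the fix allows for it. None of these objections reconciles the two ITT definitions.

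**Conclusion.** The point holds, as a minor one with two parts of unequal size. The main part is an outright contradiction: 9.3 labels a completer set as ITT, against 9.4.2. The overstatement is about 1 to 4 points of remission difference, the same with or without replacement; replacement would only refill the arm to 60 and so hide the loss. This rests on 5 to 20% non-starters who all lack later data and remit at 5%, starters remitting at 25%, and control losses unrelated to outcome. It shrinks as more non-starters attend the assessments.

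The secondary part is that 7.2 leaves the allocation of a replacement open. Its effect is 0.05 to 0.7 points if replacements bypass the sequence and everyone is kept, and zero if new recruits are randomised 1:1. The contradiction is certain from the text; the sizes are illustrative.

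**What to change.** 1. **9.3:** define ITT as in 9.4.2: all randomised participants as allocated, with no requirement for 6- or 18-month data.
2. **7.2:** state that randomised participants are not replaced; that those who do not start stay in the ITT set and are invited to the 6- and 18-month assessments; and that any additional recruits enter only through the existing 1:1 stratified sequence, the decision being made without sight of outcome data.
3. **9.4.2:** include programme start or adherence status in the imputation model for the intervention arm, or add a sensitivity analysis imputing missing non-starters at the control-arm rate. If few non-starters have 6-month data, start status can inform little and the sensitivity analysis is the more useful of the two.
4. **Per-protocol:** reconcile main session completed (9.3) with at least 70% adherence (9.4.2, 9.4.3) before using either to describe the effect in people who started.

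**Cost.** These are text changes plus one analysis. Against replacing and keeping everyone, power falls by about 1, 2, 4 and 5 points at 5, 10, 15 and 20% non-starters if nobody is added (for example 80.1 − 74.7 = 5.4). Randomising 3, 6, 9 or 12 extra people per arm more than recovers this, at 6 to 24 recruits in all and a change to the total of 120 in 9.2. If the 15% loss in 9.2 comes on top with no gain from imputation (60 × 0.85 = 51 per arm), power without replacement is about 79, 75, 72 and 68%, which is worth knowing before deciding whether to add recruits.
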